6.3.2 Treatment Period

During the two-year period, the subject will be followed by visits at months 2, 4, 6, 8, 10, 12, 15, 18, 21 and 24 according to Table 5. For operational purposes, months can be converted to days as follows (Table 6):

Table 6: Conversion of Months to Days

Month	0	2	4	6	8	10	12	15	18	21	24
Day	0	61	122	182	243	304	365	456	547	638	730

At the visits, blood samples for eGFR, plasma oxalate and safety labs will be taken. At each visit, vital signs will be taken and subjects will have a physical examination (see sections 11.7 and 11.8 for details).

Subject Quality of Life will be evaluated using a questionnaire at months 6, 12, 18 and 24.

Echocardiography (STE and traditional) will be performed at months 6, 12, 18 and 24. Ultrasound of the kidney will be done once every 12 months.

Subjects will be asked to provide five 24-hour urine samples (months 4, 8, 12, 18 and 24) and four faecal samples (months 6, 12, 18 and 24) during the treatment period. These collections will be done at the subject's home and should be scheduled in connection with the visit (+/- 7 days). The collections may be planned to occur during a weekend if preferred by the subject/parents.

At each visit, the subject will be assessed for the presence or absence of AEs and any changes in concomitant medications. Information on the occurrence of any stone event and related symptoms will be collected at each visit. Days missed at school/work due to a stone event will also be documented. Information on stone events will be captured by completing the Adverse Event eCRF. (Please note this is a data entry convention and does not replace the per protocol definition of an AE as defined in Section 11.1.)

For women of childbearing potential, a pregnancy test will be made at the last clinical visit.

The subject will receive shipment of study drug once every second week. Remaining study drug and empty containers will be returned to the clinic or site pharmacy continuously during the study at the clinic visits, as soon as new supply for the current treatment weeks has been received. The final return of study drug/empty containers will be done at clinic visit month 24.

In case any acute kidney stone event should occur during the study period, the subject should be treated according to standard hospital care. The subject should not attend a visit if they are experiencing an acute kidney injury/stone event since this may affect study values (particularly the eGFR value). When the event has been resolved, the patient can be rescheduled at the investigator's discretion to the study timetable.

The ePHex study defined blind data will remain blind in the ePHex-OLE study until the ePHex study results have been released.

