Investigational Product, Dosage and Mode of Administration:

The study drug consists of Oxabact. The dose will be administered orally twice daily as one enteric-coated size-4 capsule with breakfast (in the morning) and dinner (in the evening). The dose will be NLT 10^9 colony forming units (CFU) per capsule.

Duration of Treatment:

Subjects will be treated with Oxabact for 24 months.

Criteria for Evaluation:

Efficacy evaluation will be based on the following parameters:

Primary Endpoint

Change from baseline in kidney function (eGFR) after 12 and 24 months of openlabel Oxabact treatment.

Key Secondary Endpoints

- Change from baseline in total plasma oxalate concentration after 12 and 24 months of open-label Oxabact treatment
- ❖ Frequency of kidney stones events after 12 and 24 months of open-label Oxabact treatment. Stone events are defined as:
 - o Subject- or investigator-reported symptoms, or
 - o Stone passages or removals, or
 - o Increase in number of stones assessed by ultrasound.

Other Endpoints

- Change from baseline in myocardial function as measured by Speckle Tracking and traditional echocardiography
- ❖ Change from baseline in free plasma oxalate concentration
- Change from baseline in urinary oxalate excretion
- Change from baseline in grade of nephrocalcinosis as assessed by Ultrasound
- ❖ Change in number of *O. formigenes* in stool
- ❖ Association between change in number of *O. formigenes* in stool and change in total plasma oxalate concentration.

- ❖ Change from baseline in score of Quality of Life questionnaire.
- Change from baseline in markers for renal function, renal tubular capacity and inflammation:

Urine: magnesium, phosphorus, citrate, calcium, glycolate, creatinine, urea, calcium oxalate crystals, pH, osmolality and urinary volume. *Blood*: magnesium, phosphorus, citrate, calcium, BUN, ALP, bicarbonate, CRP, WBC, creatinine and cystatine C.

Safety:

Adverse events (AEs), vital signs, physical examination, hematology, clinical chemistry, urinalysis.

Statistical Methods:

Sample size

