6.3 Schedule of Assessments

The assessments to be performed during the study are described in Table 5, and the procedures are further described below.

Table 5 Schedule of Assessments

		Treatment (24 Months)								Post- treatment follow-up (4 weeks) ^{8, 9}		
Month	O ¹	2	4	6	8	10	12	15	18	21	24	
Day (+/- 7 days)	0	61	122	183	243	304	365	456	547	638	730	
Visit Number ²	0	1	2	3	4	5	6	7	8	9	10	NA
Clinic Visit	X	Х	Х	Х	Х	Χ	Χ	Х	Х	Х	Х	
Incl/Excl criteria	X											
Vital signs	Х	Х	Х	Х	Х	Х	Х	Х	Х	Х	Х	
Physical exam.	Х	Х	Х	Х	Х	Х	Х	Х	Х	Х	Х	
Conc. Med.	Х	Х	Х	Х	Х	Х	Х	Х	Х	Х	Х	Х
eGFR ³	Х	Х	Х	Х	Х	Х	Х	Х	Х	Х	Х	
Plasma Oxalate	Х	Х	Х	Х	Х	Х	Х	Х	Х	Х	Х	
Stone events ^{4,}	Х	Х	Х	Х	Х	Х	Х	Х	Х	Х	Х	Х
Echocard.⁵	Х			Х			Х		Х		Х	
Ultrasound	Х						Х				Х	
Safety Labs ⁶	Х	Х	Х	Х	Х	Х	Х	Х	Х	Х	Х	
Stool	Х			Х			Х		Х		Х	Х
24-hour urine	Х		Х		Х		Х		Х		Х	
Quality of Life	Х			Х			Х		Х		Х	
Pregancy test ⁷	Х										Х	
Review Adverse	Х	Х	Х	Х	Х	Х	Х	Х	Х	Х	Х	Х
events												
Drug dispense/ Accountability	Х	Х	Х	Х	Х	Х	Х	Х	Х	Х	Х	

¹ Month 0 (Visit 0; refererence time point) will be the same as the last visit (Week 52) in ePHex. For echocardiography of the heart and ultrasound of the kidneys, week 48 measurements in ePHex are considered Month 0. If there is no seamless transition (delay >1 month) from ePHex, a new clinic visit 0 (Month 0) will take place with applicable measurements prior to first dose of open label Oxabact and further assessments should follow according to schedule. ² Visit window during treatment period +/- 7 days. In the case of an acute kidney injury occurring close to a scheduled visit, the visit will be rescheduled to ensure that the AKI does not adversely affect values (especially for eGFR). The days on which each visit should occur are detailed in Table 6.

³As determined by the Schwartz equation for children (age below 18), and CKD-EPI equation for adults (age 18 or above) based on serum creatinine.

⁴ Kidney stone events and related symptoms will be captured at every visit, including events in between visits.

⁵ Echocardiography to be done within +/- 2 weeks of the clinic visit at months 6, 12 and 18. If the images fail quality criteria, the examination will be repeated within 4 weeks.

 $^{^{\}rm 6}\,\text{Safety}$ Labs will include blood and urine sampling.

⁷ If applicable.

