6.3.3 Post-treatment follow-up

Previous clinical experience with Oxabact suggests that the bacteria only transiently colonise the gastrointestinal tract and fecal recovery generally drops below detectable levels one to two weeks after end of study treatment (Hoppe et al. 2006).

A post-treatment safety follow-up will cover a duration of 4 weeks after the last dose of study treatment. The follow-up will be performed as a telephone call maximum three working days after the end of the safety follow-up period. The subject will be asked for any AEs (incl. kidney stone events) appearing after end of last dose of study treament. Additionally, any AEs that were present at the last completed study visit should be followed-up. Concomitant medication taken during the safety follow-up period should also be recorded.

Adverse Drug Reactions, which are unresolved at the time of safety follow-up call, should be followed by the Investigator until the event has resolved or, if persistent, has been assessed as chronic or stable.

Subjects will provide a post-treatment follow-up stool sample 4 weeks (plus maximum 3 working days) after intake of last dose of study drug.

End of study is defined as when the safety follow-up telephone-call and the post-treatment stool sample have been completed.

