grade 0: no echogenicity

grade 1: mild echogenicity around medullary pyramid borders

grade 2: moderate echogenicity around and inside pyramids

grade 3: severe echogenicity of entire pyramids

Grades and shifts will be summarized for left and right kidney separately. In addition, shifts will be classified (and presented) following the addendum referred to in section 11.1. Shift tables will be presented as a crosstabulation comparing baseline and 12/24 months values.

Stool

Data collected for *O.formigenes* in stool (as genotype 1 and genotype 2) will only have measurable values if above the Limit of Detection (LOD). Values below the LOD will be replaced for calculation purposes in descriptive statistics, plots and statistical analyses (see section 11.1). The proposed analyses will only be performed if there is a limited amount (<15%) of data below LOD present on-treatment. The values will be presented as '< LOD' in the listings.

Note that in case of a provided actual value lower than the LOD, it will be presented and used as is and not imputed.

Based on previous studies, it is expected that the number of subjects positive for genotype 2 at screening/baseline and throughout the study will be very low. Therefore, in case genotype 1 or 2 is not detectable in the majority of data (see above), the analysis for that genotype will not be performed and data for that genotype will then be limited to a listing. All descriptive statistics and plots will be done separately on number of *O. formigenes* genotype 1 and 2 respectively, if applicable.

Descriptive statistics will be used to present the observed and change from baseline values per treatment group and overall over time, using two baselines. Change in number of *O. formigenes* stool will be based on number of *O. formigenes* at month 24 compared to baseline in the O - O group versus the P - O group. The measurement at month 12 will be used as supportive data.

Analyses on the total number of *O. formigenes* (i.e. the sum of genotype 1 and genotype 2) may be done as post-hoc analyses, and this depends upon the number of values <LOD.

Quality of Life questionnaires

Quality of life scoring is assessed with the questionnaires SF36V2 (for adults ≥ 18 years) or CHQ/PF50 (for children ≥ 5 years). For children younger than 5 years of age, it is likely that no information from the questionnaire is available, and data will remain missing.

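### The ±7-day home stool window also applies at Month 24, so a sample taken after dosing has ended can stand as the reference value for change in O. formigenes

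*Protocol*

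**What the plan says.** Protocol 6.3.2 asks for "four faecal samples (months 6, 12, 18 and 24) during the treatment period". The next sentence sets the timing for stool and 24-hour urine together: "These collections will be done at the subject's home and should be scheduled in connection with the visit (+/- 7 days". The same window serves all four stool time points.

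Three statements bear on when dosing ends. The synopsis says "Subjects will be treated with Oxabact for 24 months". Protocol 6.3.2 adds "The final return of study drug/empty containers will be done at clinic visit month 24". The footnote to Table 5 allows the visit itself to move: "Visit window during treatment period +/- 7 days".

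Protocol 6.3.3 describes the bacteria as transient colonisers and reports that "fecal recovery generally drops below detectable levels one to two weeks after end of study treatment". It then schedules a separate off-drug stool sample 4 weeks after the last dose.

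SAP 7.6.3 (Stool) defines the change in number of O. formigenes from the count "at month 24 compared to baseline in the O - O group versus the P - O group". Of the earlier sample it says "The measurement at month 12 will be used as supportive data". The section runs the proposed analyses only if less than 15% of on-treatment data are below the limit of detection (LOD). It gives no rule that compares the collection date with the last dose.

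**The concern.** At months 6, 12 and 18 dosing continues through the whole window, so a two-sided window does no harm. At Month 24 dosing appears to stop at the visit. The second half of the window then falls in the period when the protocol expects counts to drop. A site could collect within the stated ±7 days and still deliver a post-dose sample under the Month 24 label.

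Three things are at stake:

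- The Month 24 count, which the SAP treats as the reference value, would be lowered by an amount that depends on the collection day.
- The plot of stool count against plasma oxalate would pair some off-drug counts with plasma oxalate taken at the clinic visit.
- Late values below LOD could be counted as on-treatment when the SAP decides whether to run the stool analyses at all.

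Protocol 10.6.1 regards the stool count as an important pharmacodynamic check, so a cheap way to protect it is worth having.

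**Working it through.** The plan states no figure to reproduce here. The check is day arithmetic on the stated windows, followed by a sizing of the consequences.

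**Inputs.** Month 24 is Day 730 (Protocol Tables 5 and 6). The visit window is ±7 days (Table 5 footnote). The collection window is ±7 days around the visit (Protocol 6.3.2). Time to undetectable is 7 to 14 days (Protocol 6.3.3). About 16 subjects were planned, with 12 at Month 12 and 9 at Month 24 (Protocol 12.2). SAP 2.4 reports 18 included.

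**1. Range of permitted days.**
- Visit: 730 − 7 to 730 + 7 = Day 723 to 737.
- Stool sample: 723 − 7 to 737 + 7 = Day 716 to 744.

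**2. Time off drug.**
- If the last dose is on the visit day, a permitted sample is 0 to 7 days off drug. The upper end meets the early end of the 7-to-14-day range.
- If dosing stopped on Day 730 and the visit fell on Day 737 (an assumption, as an outer bound), the latest sample is 744 − 730 = 14 days off drug.
- Days +1 to +7 are 7 of the 15 permitted days (−7 to +7). This is a share of the window. It is not a forecast of how many samples will be late.

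**3. Weight of one late sample.** With 9 completers, 1/9 = 11% of the Month 24 data. If all 18 subjects reached Month 24, 1/18 = 5.6%.

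**4. The 15% LOD limit**, counting extension-study samples only:
- 18 subjects with all four samples: 18 × 4 = 72, and 0.15 × 72 = 10.8. Eleven values below LOD (11/72 = 15.3%) would breach the limit, which is 11 of the 18 Month 24 samples.
- With the planned dropout, about 14 + 12 + 10.4 + 9 = 45.4 samples (months 6 and 18 interpolated), and 0.15 × 45.4 = 6.8. Seven values would breach it, which is 7 of the 9 Month 24 samples.

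Late samples alone would therefore have to be most of the Month 24 set to breach the limit. They matter more if other values are already below LOD. If on-treatment samples from ePHex also count, the denominator is larger and the effect smaller.

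**5. How the plan treats comparable cases.** For echocardiography, Table 5 gives the ±2-week window for months 6, 12 and 18 only, and Protocol 10.4 excludes visit 10 from the quality repeat. For stone events, SAP 7.6.2 defines the treatment period as first to last dose. Stool has neither a final-visit exception nor a dose-date rule.

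**The case against.** The strongest reply is that the protocol already says what it wants. Protocol 6.3.2 and 4.6.1 place the four samples within the treatment period, and Table 5 puts Month 24 stool under treatment, with the off-drug sample in its own column. This stands as evidence of intent, and it rules out reading the plan as endorsing washout samples. It does not enforce the intent, because the window in the next sentence is unqualified.

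The last-dose day is indeed inferred. Table 5 still marks the combined drug dispensing and accountability row at Month 24, and Protocol 8.3 lets unused drug come back at a later visit in some cases. But nothing visible provides for dosing after the Month 24 visit.

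A reader might turn the one-to-two-week statement into a daily loss. A straight-line fall in log10 count would lose 50–100% of the excess over the detection limit by day 7. The documents do not support that as an estimate. The statement rests on a 2006 publication that Protocol 4.4.1 cites for OC3a at not less than 10^7 CFU. The study drug is OC5 at not less than 10^9 CFU, with better recovery than OC3b (Protocol 4.5.2), and no OC5 decay figure is given. The direction holds; the size is unknown.

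A reader might also infer a bias between O-O and P-O. Both groups take open-label drug to Month 24 under the same window, so nothing points to a differential effect. Nor does the point extend to 24-hour urine, for which no washout figure is given. It cannot be said that withdrawal samples are often taken after the last dose: Protocol 7.4 only places those assessments at the time of withdrawal.

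Finally, other safeguards may exist. SAP section 5 identifies excluded values before database lock, and the LOD limit refers to on-treatment data. SAP Addendum 1 and the Patient Handbook were not available and may hold a rule. Such a rule could prevent mislabelling, but a SAP rule could not recover an on-drug sample that was collected late.

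**Conclusion.** The point holds in a limited form. The stated window permits a Month 24 stool sample up to 7 days after the visit at which treatment appears to end, and the visible SAP text would label it Month 24. Late samples would lower Month 24 counts in both groups and blur the graphical association with plasma oxalate. They could also count towards the 15% below-LOD limit.

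This rests on the inferred last-dose day, on washout experience from an earlier product, and on no date rule existing in the unseen addendum. How many samples would be late is unknown.

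The reach is small. Stool count is an other endpoint, evaluated descriptively. Months 6, 12 and 18 remain on drug and are summarised over time. The primary and key secondary endpoints are untouched. If ePHex is negative and this study closes early, SAP 7.1 limits efficacy reporting to the primary and key secondary endpoints, so the stool analysis falls away. The change is still worth making because it is cheap and removes an avoidable downward bias at the reference time point.

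**What to change.** **Protocol 6.3.2.** Make the Month 24 stool window one-sided: the 7 days up to and including the day of last dose. Keep ±7 days at the other visits. Repeat the instruction in the Patient Handbook.

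**SAP 7.6.3.** Compare each stool collection date with the last dose date. Summarise as Month 24 on-treatment only samples taken no later than one day after the last dose. List later ones as post-treatment, including any from early withdrawals, and keep them out of the 15% LOD count. The one-day tolerance is a judgement, not a figure from the documents. It allows for an evening dose followed by a morning sample.

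The inputs are already planned: subjects record collection details electronically (Protocol 6.3.4), and last dosing dates are listed (SAP 7.8.2). If the protocol can no longer be amended, the SAP rule alone still prevents mislabelling.

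The cost is one protocol sentence and one date rule, with no extra sample and no change to dosing. Home collection becomes slightly less flexible at one visit, and a late sample drops out of an already small Month 24 summary.

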6.3.3 Post-treatment follow-up

Previous clinical experience with Oxabact suggests that the bacteria only transiently colonise the gastrointestinal tract and fecal recovery generally drops below detectable levels one to two weeks after end of study treatment (Hoppe et al. 2006).

A post-treatment safety follow-up will cover a duration of 4 weeks after the last dose of study treatment. The follow-up will be performed as a telephone call maximum three working days after the end of the safety follow-up period. The subject will be asked for any AEs (incl. kidney stone events) appearing after end of last dose of study treament. Additionally, any AEs that were present at the last completed study visit should be followed-up. Concomitant medication taken during the safety follow-up period should also be recorded.

Adverse Drug Reactions, which are unresolved at the time of safety follow-up call, should be followed by the Investigator until the event has resolved or, if persistent, has been assessed as chronic or stable.

Subjects will provide a post-treatment follow-up stool sample 4 weeks (plus maximum 3 working days) after intake of last dose of study drug.

End of study is defined as when the safety follow-up telephone-call and the post-treatment stool sample have been completed.

6.3.4 Electronic Patient Reported Outcome

A web-based interface (ViedocMe) for electronic patient reported outcome (ePRO) will be used continuously during the study. Here, subjects will record details on collections of urine and faeces, as well as Quality of Life. Subjects will regularly receive reminders to record this data, and to follow study procedures with study drug and specimen collection.

6.4 Specimen Collection at Patient's Homes

Collections of faeces and urine will be performed at the subjects' home environment, and should be performed according to Table 5. The sponsor will provide collection kits and a Patient Handbook describing the collection procedures. Collection kits will either be taken home from the clinic by the subject or delivered to subjects' home by a courier. Pick-up of collections will be done by courier.

6.5 Diet

For the course of the study the subjects will be instructed to maintain their normal diet and fluid intake as prescribed under their standard clinical care. They will be asked to avoid making significant changes in their diet during the study specifically related to high oxalate foods and fluid intake. The subjects will be asked to refrain from ascorbic acid preparations or multivitamin preparations during the study.

7 SELECTION AND WITHDRAWAL OF PATIENTS

7.1 Subject Inclusion Criteria

- 1. Signed informed consent (as applicable for the age of the subject).
- 2. Participation in and completion of the ePHex study.
- 3. Subjects who had received vitamin B6 during the ePHex study should maintain a stable dose. Subjects not receiving vitamin B6 during the ePHex study must be willing to refrain from initiating pyridoxine during study participation.

7.2 Subject Exclusion Criteria

- 4. Inability to swallow size 4 capsules.
- 5. Use of antibiotics to which *O. formigenes* is sensitive.
- 6. Current treatment with a separate ascorbic acid preparation.
- 7. Pregnant women (or women who are planning to become pregnant) or lactating women.
- 8. Women of childbearing potential who are not using adequate contraceptive precautions.
- 9. Presence of a medical condition that the Investigator considers likely to make the subject susceptible to adverse effect of study treatment or unable to follow study procedures or any condition that is likely to interfere with the study drug mechanism of action (such as abnormal GI function).
- 10. Participation in any interventional study of another investigational product, biologic, device, or other agent or not willing to forego other forms of investigational treatment during this study.

7.3 Contraceptive Precautions

The following requirements should be followed for women of childbearing potential.

- 1. Females of childbearing potential will be included if they are either sexually inactive (sexually abstinent for 14 days prior to the first dose continuing through 28 days after the last dose), or using one of the following highly effective contraceptive methods (i.e., results in <1% failure rate when used consistently and correctly) during this trial:
 - a. intrauterine device (IUD);
 - b. surgical sterilisation of the partner (vasectomy for 6 months minimum);
 - c. combined (oestrogen or progestogen containing) hormonal contraception associated with the inhibition of ovulation (either oral, intravaginal, or transdermal);
 - d. progestogen only hormonal contraception associated with the inhibition of ovulation (either oral, injectable, or implantable);
 - e. intrauterine hormone releasing system;
 - f. bilateral tubal occlusion.

Sexual abstinence is considered a highly effective method only if defined as refraining from heterosexual intercourse during the entire period of risk associated with the study treatments. In this trial abstinence is only acceptable if in line with the subjects preferred and usual lifestyle.

Periodic abstinence (calendar, symptothermal, post-ovulation methods), withdrawal (coitus interruptus), spermicides only, and lactational amenorrhoea method (LAM) are not acceptable methods of contraception. As well, female condom and male condom should not be used together.

- 2. Females of childbearing potential agree to remain sexually inactive or to keep the same birth control method for at least 28 days following the last dose.
- 3. A female of non-childbearing potential must have undergone one of the following sterilisation procedures at least 6 months prior to the first dose:
 - a. hysteroscopic sterilisation;
 - b. bilateral tubal ligation or bilateral salpingectomy;
 - c. hysterectomy;
 - d. bilateral oophorectomy;

or be postmenopausal with amenorrhea for at least 1 year prior to the first dose and follicle stimulating hormone (FSH) serum levels consistent with postmenopausal status.

Since the study drug consist of commensal bacteria, which are a natural part of the microbiota, the risk of excretion via the semen or any negative effects from such excretion is highly unlikely. Therefore, no requirement for contraception is applied for male subjects.

Females of childbearing potential will have a pregnancy test at the end of the study. Additional information concerning participants becoming pregnant during the study can be found in Section 11.9.

